## LIST OF ABBREVIATIONS

Abbreviation	Definition
AE	adverse event
AESI	adverse event of special interest
ANCOVA	analysis of covariance
AR	adverse reaction
bAb	binding antibody
BMI	body mass index
CI	confidence interval
CDC	US Centers for Disease Control and Prevention
CMQ	Customized MedDRA Query
COVID-19	coronavirus disease 2019
CRO	contract research organization
CSP	clinical study protocol
CSR	clinical study report
DHHS	Department of Health and Human Services
DSMB	Data Safety Monitoring Board
ECG	electrocardiogram
eCRF	electronic case report form
EDC	electronic data capture
eDiary	electronic diary
EoS	end of study
FAS	Full Analysis Set
FSH	follicle-stimulating hormone
GLSM	geometric least square mean
GM	geometric mean
GMFR	geometric mean fold rise
GMR	geometric mean ratio
GMT	geometric mean titer
HA	hemagglutinin
HAI	hemagglutination inhibition
IA	Interim analysis
ILI	influenza-like illness
IM	intramuscular
IP	investigational product
IRT	interactive response technology
LLOQ	lower limit of quantification
MAAE	medically attended adverse event
MedDRA	Medical Dictionary for Regulatory Activities
mRNA	messenger ribonucleic acid
nAb	neutralizing antibody
NP	nasopharyngeal
PP	Per-Protocol
PsVNA	pseudovirus neutralization assay
PT	preferred term
RT-PCR	reverse transcriptase polymerase chain reaction
SAE	serious adverse event
SAP	statistical analysis plan
SARS-CoV-2	severe acute respiratory syndrome coronavirus 2
SAS	Statistical Analysis System
SCR	seroconversion rate
SD	standard deviation

Abbreviation	Definition
SMQ	Standardized MedDRA Query
SOC	system organ class
SoA	schedule of activities
SRR	seroresponse rate
TEAE	treatment-emergent adverse event
ULOQ	upper limit of quantification
WHO	World Health Organization
WHODD	World Health Organization drug dictionary

## SUMMARY OF MAJOR CHANGES IN SAP VERSION

SAP Version	Section # and Name	Description of Change
V2.0	5.3 Per Protocol (PP) Set	Clarified existing language for conditions/medications that affect the immune response.
V2.0	6.1 General Considerations	Clarified that all subgroups are based on eCRF entries unless otherwise stated. Added definition for Baseline SARS-CoV-2 Status and added this Baseline SARS-CoV-2 Status to Table 5, as a subgrouping factor to be used in table summaries.
V2.0	6.2.2 Demographics and Baseline Characteristics	Added 3 categorical baseline variables: Baseline SARS-CoV-2 RT-PCR Results, Elecsys Anti-SARS-CoV-2 Results, and Baseline SARS-CoV-2 Status.
V2.0	6.3.2 Unsolicited Treatment-Emergent Adverse Events	Updated to reflect only Solicited ARs that meet SAE criteria are recorded on the Reactogenicity eCRF.
V2.0	6.4.2 Immunogenicity Analysis	Updated wording in 6.4.2.2 Analytical summaries, and added a new Table 6 to clarify the covariates used in the ANCOVA analyses. Renumbered later tables and added clarifying language to Table 7. Removed bar-plot of ANCOVA-based GMT.
V3.0	6.2.4 Prior and Concomitant Medications	“Antipyretic or analgesic medication within 28 days postinjection” item removed
V3.0	6.4.2.1. Analysis of Secondary Immunogenicity Endpoints	For GMFR, values below LLOQ imputed to LLOQ
V3.0	6.4.2.2 Analytical summaries	Added D181 GMT/GMR; added figure for D181 GMFR, SCR, SRR, and GMR
V3.0	6.5.1.2 SARS-CoV-2 Infection	Asymptomatic SARS CoV 2 infection language removed
V3.0	Appendix H TEAE of Specifical Interest by SMQ	SMQ table updated
V4.0	Global update	Part 2 added to the SAP per protocol amendment 1 dated 16-Jan-2024 and protocol amendment 2 dated 14 Mar 2024
V5.0	3.6.4.1. Primary Immunogenicity Endpoints	Updated the “Covariate(s)” column in Table 14, by adding “Log-transformed baseline antibody value” for all rows.

## 1. Introduction

This statistical analysis plan (SAP), which describes the planned analyses for Study mRNA-1083-P101, is based on the most recent approved clinical study protocol amendment (CSP), dated 14-MAR-2024, and the most recent approved electronic case report form (eCRF), dated 31-MAY-2024.

In addition to the principal features of analyses for this study described in Section 9 of the protocol, this SAP provides statistical analysis details/data derivations. It also documents modifications or additions to the analysis plan that are not “principal” in nature and result from information that was not available at the time of protocol finalization.

Study mRNA-1083-P101 is a phase 1/2, randomized, observer-blind, active-control study to evaluate the safety, reactogenicity, and immunogenicity of mRNA-based Influenza and SARS-CoV-2 multi-component vaccines in healthy adults.

The study is divided into 2 parts: Part 1 and Part 2. Part 1 (Phase 1/2) includes adults who are 18 to <80 years and Part 2 (Phase 2 Extension) includes adults who are 18 to <50 years.

Approximately 1744 participants will be enrolled in the overall clinical trial.

PPD Biostatistics and Programming team, designee of Moderna Biostatistics and Programming department, will perform the statistical analysis of the safety, reactogenicity, and immunogenicity data; Statistical Analysis System (SAS) Version 9.4 or higher will be used to generate all statistical outputs (tables, figures, listings, and datasets). The SAP will be finalized and approved prior to the primary analysis clinical database lock and treatment unblinding for the study. If the methods in this SAP differ from the methods described in the protocol, the SAP will prevail.

In this document, study vaccination, intervention administration, injection of investigational product (IP)/investigational vaccine, dosing, and injection are used interchangeably. Treatment group, investigational treatment arm, vaccination group are used interchangeably.

## 2. Part 1

### 2.1. Study Objectives

#### 2.1.1. Primary Objectives

The primary objective is to evaluate the safety and reactogenicity of study intervention administration across study treatment arms.

#### 2.1.2. Secondary Objectives

The secondary objectives are:

- To evaluate the humoral immune responses to vaccine-matched strains for influenza and SARS-CoV-2 across study treatment arms at Day 29
- To evaluate the humoral immune responses to vaccine-matched strains for influenza and SARS-CoV-2 across study treatment arms at all evaluable humoral immunogenicity time points

#### 2.1.3. Exploratory Objectives

The following exploratory objectives may be assessed:

- To evaluate the humoral immune responses to vaccine-mismatched strains for influenza and SARS-CoV-2 across study treatment arms
- To evaluate the humoral immune responses against vaccine-matched and vaccine-mismatched strains for influenza and SARS-CoV-2 across study treatment arms
- To evaluate the cellular immune responses against influenza and SARS-CoV-2 in a subset of participants
- To further characterize the immune response to influenza and SARS-CoV-2 across study treatment arms
- To assess the occurrence of clinical influenza and COVID-19 in study participants and characterize their immune response to infection and viral isolates

## 2.2. Study Endpoints

### 2.2.1. Primary Endpoints

The primary objective will be evaluated by the following endpoints:

- Solicited local and systemic adverse reactions (ARs) through 7 days after injection
- Unsolicited AEs through 28 days after injection
- Unsolicited severe adverse events through 28 days after injection
- Unsolicited medically attended adverse events (MAAEs) from Day 1 to Day 181/End of Study (EoS)
- Unsolicited adverse events of special interest (AESIs) from Day 1 to Day 181/EoS
- Serious adverse events (SAEs) from Day 1 to Day 181/EoS
- Unsolicited AEs leading to discontinuation from Day 1 to Day 181/EoS

### 2.2.2. Secondary Endpoints

The secondary objective will be evaluated by the following endpoints:

- Geometric mean titer (GMT) and geometric mean fold rise (GMFR) at Day 29 compared with Day 1 by hemagglutination inhibition (HAI) assay for influenza and by pseudovirus neutralization assay (PsVNA) for SARS-CoV-2
- Influenza: Percentage of participants with seroconversion, defined as a Day 29 titer **CCI** if Baseline is **CCI** or a 4-fold or greater rise if Baseline is **CCI** in anti-HA antibodies measured by HAI assay
- SARS-CoV-2: Percentage of participants with seroresponse, defined as a Day 29 titer  $\geq 4$ -fold if Baseline is  $\geq$ LLOQ or  $\geq 4 \times$  LLOQ if Baseline titer is  $<$ LLOQ in neutralizing antibody (nAb) titers measured by PsVNA
- GMT and GMFR at all evaluable timepoints compared with Day 1 by HAI for influenza and PsVNA for SARS-CoV-2
- Influenza: Percentage of participants with seroconversion at all evaluable timepoints
- SARS-CoV-2: Percentage of participants with seroresponse at all evaluable timepoints

### 2.2.3. Exploratory Endpoints

The exploratory objectives may be evaluated by the following endpoints:

- GMT and GMFR at all evaluable timepoints compared with Day 1 by HAI for influenza and PsVNA for SARS-CoV-2
- Influenza: Percentage of participants with seroconversion to vaccine mismatched strains at all evaluable timepoints
- SARS-CoV-2: Percentage of participants with seroresponse to vaccine mismatched strains at all evaluable timepoints
- GMT and GMFR at all evaluable timepoints compared with Day 1 by alternative methods, including, but not limited to: microneutralization assay for influenza or ligand-binding assay for SARS-CoV-2
- Frequency, magnitude, and phenotype of virus-specific T-cell and B-cell responses measured by flow cytometry or other methods
- Perform targeted repertoire analysis of B-cells and T-cells after vaccination
- Frequency, specificities, or other endpoints to be determined for the further characterization of immune responses
- Frequency of RT-PCR-confirmed clinical influenza and COVID-19
- Assessment of immune responses to infection and viral isolates

## 2.3. Study Design

### 2.3.1. Overall Study Design

**Part 1** of the study is a Phase 1/2 randomized, stratified, observer-blind, active-control study to evaluate the safety, reactogenicity, and immunogenicity of mRNA-1083 compositions and dose levels compared with active-control vaccines mRNA-1010, mRNA-1283.222, mRNA-1273.222, and licensed active-control vaccines, Fluarix® and Fluzone® HD (Cohort A only) in healthy adults  $\geq 18$  to  $< 80$  years of age (Cohort A is in adults  $\geq 65$  to  $< 80$  years of age and Cohort B is in adults  $\geq 18$  to  $< 65$  years of age).

Approximately 1224 participants will be enrolled into 1 of 2 age cohorts: Cohort A for adults  $\geq 65$  to  $< 80$  years of age or Cohort B for adults  $\geq 18$  to  $< 65$  year of age. In Cohort A,

approximately 600 participants will be randomized (in equal allocation ratio) into the investigational treatment arms, stratified by influenza vaccine status in the most recent influenza season (received or not received since September 2022). In Cohort B, approximately 624 participants will be randomized (in equal allocation ratio) into the investigational treatment arms, stratified by 2 age groups:  $\geq 18$  to  $< 50$  years and  $\geq 50$  to  $< 65$  years of age and by influenza vaccine status in the most recent influenza season (received or not received since September 2022). Approximately 50% of the participants in Cohort B will be  $\geq 50$  to  $< 65$  years of age. Table 1 lists the details of study cohorts and dose levels for study vaccine administration. All participants will receive a single intramuscular (IM) injection of study intervention administered in a deltoid muscle on Day 1.

**Table 1 Study Arm(s) and Interventions (Part 1)**

Cohort A Arms: ( $\geq 65$ to $< 80$ years), n=50/arm, 600 total	Cohort B Arms: ( $\geq 18$ to $< 65$ years), n=52/arm, 624 total	Intervention	Total mRNA Dose (μg)	CCI	Intervention Type
NA	B1	mRNA-1083.1	100	CCI	IP
A2	B2	mRNA-1083.1	100		IP
A3	B3	mRNA-1083.1	100		IP
A4	B4	mRNA-1083.2	100		IP
A5	B5	mRNA-1083.2	100		IP
A6	B6	mRNA-1083.2	100		IP
A7	B7	mRNA-1083.3	100		IP
A8	B8	mRNA-1010	100		Non-IP experimental comparator
A9	B9	mRNA-1283.222	100		Non-IP experimental comparator
A10	B10	mRNA-1273.222	100		Non-IP experimental comparator
A11	B11	mRNA-1010	100		Non-IP experimental comparator
A12	B12	Fluarix	100		Licensed vaccine comparator
A13	NA	Fluzone HD	100		Licensed vaccine comparator

Abbreviations: HD=high dose; IP=investigational product; mRNA=messenger ribonucleic acid; NA=not applicable; SARS-CoV-2=severe acute respiratory syndrome coronavirus 2.

[figure not shown]
Total mRNA dose is rounded to the nearest CCI μg

CCI

All participants of the study will participate in a Screening period (up to 28 days before Day 1), treatment period (single dose of vaccine on Day 1), and a follow-up period (up to 6 months after

vaccination). The study schema is presented in Figure 1. Please refer to the Schedule of Activities (SoA) available in Appendix A.

**Figure 1 Study Schema (Part 1)**

Abbreviations: HD=high dose; mRNA=messenger ribonucleic acid

### 2.3.2. Statistical Hypotheses

This clinical trial does not have formal statistical hypothesis testing planned for the primary objective (safety and reactogenicity). The total sample sizes planned are considered sufficient to provide descriptive summary of the safety and reactogenicity across study treatment arms within each age Cohort for respective parts.

### 2.3.3. Sample Size and Power

The sample size for this study is not driven by statistical assumptions for formal hypothesis testing. Approximately 1224 participants will be enrolled at an evenly allocated ratio across the 12 treatment arms in Cohort A for adults  $\geq 65$  to  $< 80$  years of age and 12 treatment arms in Cohort B for adults  $\geq 18$  to  $< 65$  years of age, with 50 participants planned for each arm in Cohort A (600 participants in total) and 52 participants planned for each arm in Cohort B (624 participants in total) (Table 2). Approximately 50 participants in each group receiving an investigational injection have approximately 87% (or 92%) probability to observe at least 1 participant with an AE given the true underlying incidence rate of AE is 4% (or 5%).

**Table 2 Sample Size Determination (Part 1)**

Sample Size	True AE Rate	Probability of 0 AEs	Power to Detect at Least 1 AE
50	2.0%	36.4%	63.6%
50	3.0%	21.8%	78.2%
50	4.0%	13.0%	87.0%
50	5.0%	7.7%	92.3%

Abbreviation: AE = adverse event.

### 2.3.4. Randomization

Randomization will be performed using an interactive response technology (IRT) by a 3rd party vendor.

- In Cohort A, approximately 600 participants will be randomized (in equal allocation ratio) into the investigational treatment arms, stratified by influenza vaccine status in the most recent influenza season (received or not received since September 2022).
- In Cohort B, approximately 624 participants will be randomized (in equal allocation ratio) into the investigational treatment arms, stratified by 2 age groups:  $\geq 18$  to  $< 50$  years and  $\geq 50$  to  $< 65$  years of age and by influenza vaccine status in the most recent influenza season (received or not received since September 2022). Approximately 50% of the participants in Cohort B will be  $\geq 50$  to  $< 65$  years of age.

### 2.4. Blinding and Unblinding

The planned analyses including a potential Day 8 interim analysis and the Day 29 interim analysis are described in Section 2.6.7 of this SAP. For further details on preidentified sponsor

and CRO team members (identified by role), and the level of unblinding (treatment group level unblinding and/or subject level unblinding) at the IAs and the Final analysis, please refer to the study Data Blinding Plan.

## **2.5. Analysis Sets**

### **2.5.1. Randomization Set**

The randomization set consists of all participants who are randomly assigned. Participants will be included in the vaccination group to which they are randomized.

### **2.5.2. Full Analysis Set (FAS)**

The FAS consists of all participants who are randomly assigned and receive the study intervention. Participants will be analyzed according to the group to which they were randomized.

### **2.5.3. Per Protocol (PP) Set**

The PP Set in Part 1 consists of all participants in the FAS who comply with the injection schedule, comply with the timings of immunogenicity blood sampling to have a Baseline and at least 1 post-injection assessment at Day 29 (-7 to +14 days), have no documented infection (confirmed by RT-PCR test) of either influenza or SARS-CoV-2 on Day 1 and up to Day 29 (Day 29 immunogenicity assessment + 7 days), have no major dosing error, and have no major protocol deviations or conditions/medications that affect the immune response. The PP Set will be used as the primary analysis set for analyses of immunogenicity in Cohort A or B unless otherwise specified. Participants will be analyzed according to the group to which they were randomized.

The major dosing error ranges, available in Table 3, will be used to determine participant exclusion from the PP analysis populations:

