### 1.3. Schedule of Activities (SoA)

Table 1: Schedule of Activities (Part 1 – Phase 1/2)

Visit Number	SCRN	1	2	3	4, 5, 6, 7	8	USV
Type of Visit	C	C	C	C	SC	C	C
Month Timepoint	NA			M1	M2-M5	M6	Up to M6
Visit Day	SCRN a	D1 (Baseline) a	D8	D29	D57, D91, D121, D151	D181/ EoS	NA
Window Allowance (Days)	-28	NA	-1 to +3	-7 to +3	±5	±14	NA
Informed consent form, demographics, concomitant medications, medical history	X						
Inclusion/exclusion criteria	X	X					
Blood collection for safety laboratory samples b	X		X				
Full physical examination c	X						
Axillary lymph nodes assessment d		X					
Symptom-directed physical examination e		X	X	X		X	X
Vital sign measurements f	X	X					
Electrocardiogram g		X					
Pregnancy testing h	X	X					
Randomization		X					
Study intervention (including 60-minute, postdose observation period)		X					
Blood collection for humoral immunogenicity i		X		X		X	
Blood collection for cellular immunogenicity i		X		X			
Optional blood collection for genomics j		X					
Optional blood collection for transcriptomics j		X	X	X			
Blood sample for potential cardiac biomarker analysis k		X					
Nasal swab for virus detection l		X					X

Visit Number	SCRN	1	2	3	4, 5, 6, 7	8	USV
Type of Visit	C	C	C	C	SC	C	C
Month Timepoint	NA			M1	M2-M5	M6	Up to M6
Visit Day	SCRN a	D1 (Baseline) a	D8	D29	D57, D91, D121, D151	D181/ EoS	NA
Window Allowance (Days)	-28	NA	-1 to +3	-7 to +3	±5	±14	NA
Blood collection for SARS-CoV-2 antibodies, nucleocapsid		X					
eDiary activation for recording solicited local and systemic ARs (7 days) m		X					
Review of solicited AR eDiary			X				
Follow-up safety call n					X		
Recording of unsolicited AEs through Day 29		X	X	X			
Recording of SAEs, AESIs, MAAEs, AEs leading to discontinuation, and concomitant medications associated with these events		X	X	X	X	X	X
Recording of nonstudy vaccinations	X	X	X	X	X	X	X
Study completion						X	

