#### 10.3.8. Suspicion of SARS-CoV-2 Infection

SARS-CoV-2 should be suspected if the participant experiences any one of the symptoms listed below lasting at least 48 hours (except for fever and/or respiratory symptoms) ([CDC 2020b](#)):

- Fever (temperature  $\geq 38.0^{\circ}\text{C}$  [ $100.4^{\circ}\text{F}$ ]) or chills (of any duration, including  $\leq 48$  hours)
- Cough (of any duration, including  $\leq 48$  hours)
- Shortness of breath and/or difficulty breathing (of any duration, including  $\leq 48$  hours)
- Fatigue
- Muscle or body aches
- Headache
- New loss of taste and/or smell
- Sore throat, congestion, or runny nose
- Nausea or vomiting
- Diarrhea

Symptomatic COVID-19 is defined by the presence of one of the CDC-listed symptoms ([CDC 2020c](#)) and a positive RT-PCR test on a respiratory sample. Asymptomatic SARS-CoV-2

infection is defined as a positive RT-PCR test on a respiratory sample in the absence of symptoms or a positive serologic test for antinucleocapsid antibody after a negative test result at the time of enrollment, with the serologic assay detecting previously resolved SARS-CoV-2 infections that may have occurred between visits, and the RT-PCR to detect active viral infection at the time of a visit. If participants are confirmed to have SARS-CoV-2 infection and are symptomatic or asymptomatic, the Investigator will notify the participants' primary care physicians of the diagnosis and the local public health authorities as required per local regulations.

If the participant had known exposure to COVID-19 (eg, exposure to someone with a confirmed case of COVID-19), it will be captured in the COVID-19 exposure form, and the participant will continue to follow all remaining study assessments as scheduled. Likewise, participants with a confirmed case of COVID-19 will continue to follow all remaining study assessments as scheduled.

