#### 2.6.4.1. Secondary Immunogenicity Endpoints

- GMT and GMFR at Day 29 compared with Day 1 by HAI assay for influenza and PsVNA for SARS-CoV-2
- Influenza: Percentage of participants with seroconversion, defined as a Day 29 titer **CCI** if Baseline is **CCI** or a 4-fold or greater rise if Baseline is **CCI** in anti-HA antibodies measured by HAI assay

- SARS-CoV-2: Percentage of participants with seroresponse, defined as a Day 29 titer  $\geq 4$ -fold if Baseline is  $\geq$  LLOQ or  $\geq 4 \times$  LLOQ if Baseline titer is  $<$  LLOQ in nAb titers measured by PsVNA (or binding antibody assay)
- GMT and GMFR compared with Day 1 (Baseline) by HAI for influenza and PsVNA (or binding antibody assay) for SARS-CoV-2 at all evaluable timepoints
- Percentages of participants with seroconversion (influenza) and seroresponse (SARS-CoV-2) as defined below, at all evaluable timepoints

For the secondary immunogenicity endpoints, descriptive summaries statistics, including median, Q1, Q3, minimum, and maximum along with the number and percentage values above ( $\geq$ ) LLOQ and below ( $<$ ) LLOQ will be provided for the antibody titer values by treatment arm (available in Section 2.6.1) for the influenza and SARS-CoV-2 endpoints. In addition, the following endpoints summaries will be provided:

- Geometric mean of specific antibody titers (GMT) with corresponding 2-sided 95% CI at each time point
- Geometric mean fold rise (GMFR) of specific antibody titers with the corresponding 2-sided 95% CI at each post-Baseline time point over pre-injection Baseline at Day 1,

Listing presenting the antibody level, for each specific strain of influenza and SARS-CoV-2 will be provided. The ratio of post-Baseline/Baseline, LLOQ and ULOQ will be presented as well. An additional listing will be provided for participants with Influenza or SARS-CoV-2 infections.

Reverse Cumulative Distribution Function for each specific strain of influenza and SARS-CoV-2 will be provided. The box plot for GMT and GMFR will be provided at all evaluable timepoints. The bar plot for GMFR at Day 29 will also be provided.

$$2^{\left\{ \frac{\sum_{i=1}^n \log_2(t_i)}{n} \right\}} = 2^{\left\{ \frac{\sum_{i=1}^n \log_2(v_{ij}/v_{ik})}{n} \right\}} = 2^{\left\{ \frac{\sum_{i=1}^n \log_2(v_{ij}) - \log_2(v_{ik})}{n} \right\}}$$

Additional descriptions will be provided by treatment arm (available in Section 2.6.1) for the following influenza and SARS-CoV-2 endpoints:

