- Percentages of participants with seroconversion (influenza) and seroresponse (SARS-CoV-2) with the corresponding 2-sided 95% CI at each post-Baseline time point,

- Percentages of participants with a GMFR results  $\geq 2$ , and  $\geq 4$  with the corresponding 2-sided 95% CI at each post-Baseline time point.

For participants in the groups receiving mRNA-1083, mRNA-1010 or influenza injections, seroconversion rate from Baseline will be provided with a 2-sided 95% CI using the Clopper-Pearson method at each post-Baseline time point. Rate of seroconversion is defined as the proportion of participants with either a pre-vaccination HAI titer CCI and a post-vaccination HAI titer CCI or a pre-vaccination HAI titer CCI and a minimum 4-fold rise in post-vaccination HAI antibody titer.

For participants in the groups receiving mRNA-1083, mRNA-1283.222 or mRNA-1273.222, seroresponse rate will be summarized for planned post-Baseline visits, including the 2-sided 95% CI using the Clopper-Pearson method. Rate of Seroreponse for SARS-CoV-2 is defined as a  $\geq 4$  fold rise in nAb titer from Baseline in those with Baseline titer  $\geq$  LLOQ, or a post-Baseline titer  $\geq 4 \times$  LLOQ if Baseline titer is  $<$  LLOQ.

In addition, the following analysis statistics will be provided by treatment arm (available in Table 7) at Day 29 and D181 for the following influenza and SARS-CoV-2 endpoints:

- Within Treatment Group, Model-based geometric mean titer (GMT) with the corresponding 95% CI,
- Between Treatment Group, Pair-wise geometric mean ratios (GMR) with the corresponding 95% CI

The model-based GM titer will be estimated based on an analysis of covariance (ANCOVA) model, and it will be modelled separately for Cohort A and Cohort B. In the ANCOVA model, the log-transformed antibody titer at a post-Baseline timepoint (Day 29 or Day 181) are treated as a dependent variable, with the treatment group as an explanatory variable and covariates listed in Table 6 below for different assays, Cohorts and subgroups:

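### Part 1: the Per Protocol Set stops excluding infection about a week after the Day 29 draw, yet the same set is used for Day 181 titers, so titers raised by later infection are pooled with vaccine-induced ones

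*SAP*

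**What the plan says.** The Part 1 Per Protocol definition in SAP 2.5.3 requires that participants "have no documented infection (confirmed by RT-PCR test) of either influenza or SARS-CoV-2 on Day 1 and up to Day 29". The parenthesis that follows fixes the cut-off: "up to Day 29 (Day 29 immunogenicity assessment + 7 days". The draw itself must meet "at least 1 post-injection assessment at Day 29 (-7 to +14 days". The set's role is general: "The PP Set will be used as the primary analysis set for analyses of immunogenicity in Cohort A or B unless otherwise specified". SAP 2.6.4 repeats that it is the primary population for immunogenicity, and no separate Day 181 set is defined.

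SAP 2.6.4.1 gives descriptive GMT, GMFR, seroconversion and seroresponse rates at each post-baseline time point. It then states that "the following analysis statistics will be provided by treatment arm (available in Table 7) at Day 29 and D181", meaning ANCOVA-based GMTs and pairwise GMRs. Bar plots of GMR, GMFR and the two rates are also planned at Day 181. The ANCOVA covariates in SAP Table 6 are age group and influenza vaccine status, or none; there is no infection term.

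Later infections appear in two places. SAP 2.6.5.1 to 2.6.5.3 tabulate RT-PCR results and confirmed illness by vaccination group on the FAS through end of study. SAP 2.6.4.1 adds: "An additional listing will be provided for participants with Influenza or SARS-CoV-2 infections".

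**The concern.** By removing participants infected before the Day 29 draw, the plan accepts that natural infection makes a titer unsuitable as a measure of vaccine response. A Day 181 titer drawn after an infection has the same problem, but nothing sets it aside. It enters the arm's Day 181 GMT and GMFR, and may count as a seroconversion or seroresponse.

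A uniform infection rate would raise every arm's absolute Day 181 figures. Unequal rates would also shift the GMR, lowering it for the arm with fewer infections.

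The infection dates needed to examine this are available. Protocol 8.3.7.1 and the Part 1 Schedule of Activities call for a nasal swab within 7 days of suspected influenza-like illness or COVID-19 through study completion, and SAP 2.6.5.2 derives a start date for confirmed influenza illness.

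**Working it through.** **Plan's own figure.** The only sample-size figure concerns adverse events: 1 − 0.96^50 = 87.0%, which agrees with Protocol Table 8. It does not bear on this point. No Day 181 precision or effect size is stated.

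**Length of the uncovered period.** Inputs are from SAP 2.5.3.
- On-time draw: 29 + 7 = study day 36; 181 − 36 = 145 days uncovered.
- Earliest draw: 29 − 7 + 7 = day 29; 181 − 29 = 152 days.
- Latest draw: 29 + 14 + 7 = day 50; 181 − 50 = 131 days.

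**Effect on GMT and GMFR.** Let f be the fraction of an arm infected after the cut-off and before the Day 181 draw. Let k be the geometric mean factor by which infection multiplies their Day 181 titer. The mean log titer rises by f × log k, so the GMT is multiplied by k^f. The GMFR is multiplied by the same factor because baseline is unchanged. The documents give neither f nor k; both are assumed over a range:

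| f | k=2 | k=4 | k=8 | k=10 |
|---|---|---|---|---|
| 2% | 1.01 | 1.03 | 1.04 | 1.05 |
| 5% | 1.04 | 1.07 | 1.11 | 1.12 |
| 10% | 1.07 | 1.15 | 1.23 | 1.26 |
| 20% | 1.15 | 1.32 | 1.52 | 1.58 |

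**Effect on GMR.** The multiplier is k^(f_treatment − f_control), so equal infection rates leave the GMR unchanged. A 5-point difference at k=8 moves it by 8^0.05 = 1.11. With 5% infected on treatment and 15% on control, it is 2^(−0.10) = 0.93 to 10^(−0.10) = 0.79.

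**Effect on SCR and SRR.** Let s be the true Day 181 rate. If infection is unrelated to whether a participant would otherwise have responded, the rate rises by at most (1 − s)f. At s = 40% the rise is 0.6f, giving at most 43%, 46% and 52% for f = 5%, 10% and 20%.

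**Number of titers involved.** With 50 per arm in Cohort A, 50f is 1 participant at f=2% and 10 at f=20%.

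**The case against.** The strongest reply is that observed titers regardless of later infection are a legitimate target. The stated objective is humoral response at all evaluable time points, and nothing in the SAP claims that Day 181 isolates the vaccine's contribution. That stands as a reason to keep the planned analysis, but not as a reason to omit a supportive one beside it.

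Little depends on these tables. The study plans no formal hypothesis testing (SAP 2.3.2, 2.3.3), SAP Table 7 labels the Part 1 comparisons exploratory, and rate differences between arms are planned at Day 29 only. Part 1 enrolled in April to May 2023, so Day 181 fell around October to November 2023, when the Phase 3 study was already enrolling (Protocol 2). The GMR shift is also modest against sampling error. Assuming an SD of 0.8 to 1.2 on the natural-log scale and 50 per arm, the 95% CI factor is exp(1.96 × SD × √(2/50)), or 1.37 to 1.60, against a shift of 1.11. All this limits the importance of the point.

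Setting infected participants aside can itself select, because infection is a post-vaccination outcome. If low responders are infected more often, those who remain look better. This is why the addition should be supportive only.

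The Per Protocol definition also excludes unspecified conditions affecting immune response. That could be stretched to later infection, but it is undefined, whereas the infection clause has its own end date.

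A reader might infer more than the documents support:
- That later infections are merely listed. They are also tabulated by arm on the FAS, with time periods.
- That the SAP presents Day 181 as vaccine durability. It does not use that word.
- That rates could rise by the full f points. That would need every infected participant to be an otherwise non-responder, which nothing suggests.
- That the same remedy works across the trial. Part 2 schedules no swab after Day 1.
- That serological infection can never be identified after enrollment. Protocol 10.3.8 does include "a positive serologic test for antinucleocapsid antibody after a negative test result at the time of enrollment", and "Blood collection for SARS-CoV-2 antibodies, nucleocapsid" is scheduled on Day 1 only. But Day 181 serum is drawn, Protocol 10.1.9 permits further humoral assays on remaining samples, and SAP 2.6.5.3 does not use the asymptomatic definition.

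**Conclusion.** The point holds for Part 1 as a gap in the Day 181 antibody analysis. The infection exclusion ends at the Day 29 assessment plus 7 days, the same analysis set is used at Day 181, and collected infection dates are not linked to the titers. About 131 to 152 days are uncovered, taking Day 181 at its nominal date.

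The size of any distortion cannot be taken from the documents. Over the assumed ranges (2 to 20% infected, 2- to 10-fold boost) the arm GMT is inflated by about 1% to 58%; at 5 to 10% infected and a 4-fold boost, by 7% to 15%. These figures use a single k, whereas influenza is reported by strain and infection need not boost all four strains equally. A GMR is biased only if infection, or the size of the boost, differs between arms; the documents do not show that it does. No primary output, sample size or formal conclusion is affected.

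**What to change.** In SAP 2.6.4.1, keep the planned Day 181 analysis and add, for Part 1 only, a supportive Day 181 GMT, GMFR, SCR, SRR and model-based GMR in the Per Protocol Set. In it:
- set aside titers to the infecting virus drawn after an RT-PCR-confirmed infection that occurred beyond the Day 29 window;
- keep titers to the other virus;
- report by arm the number of Per Protocol participants whose titers are set aside, since the existing infection tables are on the FAS.

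State the limits with the tables: slightly fewer participants, possible selection because infection follows vaccination, and asymptomatic or unswabbed infections left in.

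The cost is a paragraph of SAP text and one further set of Part 1 Day 181 tables from data already collected. There is no new visit or blood draw. Anti-nucleocapsid testing of stored Day 181 serum in baseline-negative participants would pick up some of the missed SARS-CoV-2 infections; it is optional and not part of the required change.
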